NAC is a naturally occurring amino-acid that has been used safely for decades as an antioxidant agent and as an antidote for acetaminophen overdose. Due to its benign safety profile, NAC is available as an over-the-counter medication at a cost of less than 25 cents a day. More recently, NAC has been demonstrated to be a glutamate modulating agent. NAC is converted to cystine, a substrate for the glutamate/cystine antiporter located on glial cells. The uptake of cystine by glia causes glial release of glutamate into the extrasynaptic space, where it appears to stimulate inhibitory metabotropic glutamate receptors on glutamatergic nerve terminals and thereby reduces the synaptic release of glutamate (Moran, McFarland et al. 2005). NAC has been recently demonstrated in randomized, double-blind, placebo-controlled studies to be effective for the treatment for bipolar depression and schizophrenia (Berk, Copolov et al. 2008; Berk, Copolov et al. 2008). NAC has also been demonstrated in double-blind, placebo-controlled studies to effectively reduce the symptoms of trichotillomania, a disorder that is considered to be on the OC spectrum and is often comorbid with OCD (Grant, Odlaug et al.

2009). NAC has also demonstrated to be safe without significant side effects in a recent double-blind, placebo-controlled trial in children with autism (Posey, Erickson et al. 2009).

3. **Research Plan:** Provide an orderly scientific description of the study design and research procedures as they directly affect the subjects.

Subjects: Children with OCD will be recruited through the TS/OCD Clinic at the Yale Child Study Center. Inclusion and Exclusion Criteria are listed below.

Intervention: Subjects will be randomized in a ratio of 1:1 to receive treatment with NAC or placebo. NAC (or placebo) will be titrated up to a maximum dose of 2400mg/day over the course of 1 week. Subjects will take a single 600mg tablet twice a day for 1 week, and then increase to two 600mg tablets twice a day for the remainder of the 12 week study. After completion of the study all subjects receiving placebo will be offered NAC treatment for the following 12 weeks.

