Assessment: *Pre-study screening procedure:* After an initial phone screen to rule out obvious exclusions from the study protocol, potential subjects will have an initial evaluation that will be performed by a multidisciplinary clinical team. Exclusions in screening would include (1) Comorbid bipolar disorder, psychotic disorder, substance use disorder, developmental disorder or mental retardation (IQ<70), (2) asthma diagnosis requiring treatment in the last 3 months, and (3) a change in psychotropic medications or behavioral treatment for OCD within the last month. In addition to a standard clinical evaluation consisting of history, and mental status exams, subjects will receive a clinical diagnostic interview using the Kiddie-Schedule for Affective Disorders and Schizophrenia (K-SADS) (Kaufman, Birmaher et al. 1997). Additional baseline ratings will be conducted for OCD, tic, depression and anxiety severity using: 1) Children's Yale-Brown Obsessive-Compulsive Scale (CY-BOCS) (Scahill, Riddle et al. 1997), (2) Dimensional Yale-Brown Obsessive-Compulsive Scale (DY-BOCS). Additional baseline ratings

HIC#1004006623

will be conducted for OCD, tics, trichotillomania, depression and anxiety severity using (3) Yale Global Tic Severity Scale (YGTSS) (Leckman, Riddle et al. 1989), (4) ADHD Rating Scale (ADHD-RS) (DuPaul, Power et al. 1998), (5) Multidimensional Anxiety Scale for Children (MASC) (March, Parker et al. 1997), (6) Children's Depression Inventory (CDI) (Kovacs 1985), (7) Massachusetts General Hospital – Hairpulling Scale (MGH-HPS) (Keuthen, O'Sullivan et al. 1995), (8) Clinical Global Impression (CGI) scale (Guy 1976) and (9) Pediatric-Adverse Events Rating Scale (PAERS) (March, Karayal et al. 2007). The pediatric adverse events rating scale will be used to monitor safety throughout the trial. A medical assessment including vital signs, physical exam and urine drug screen and pregnancy test will be completed prior to study enrollment. The measures utilized in this study are outlined below.

Baseline Assessments	Medical Assessments	Rating scales
K-SADS	Vital Signs	CY-BOCS DY-BOCS
Psychiatric History	Physical Exam	YGTSS ADHD-RS
General Medical History	Mental Status Exam	CDI MASC
	Urine Toxicology	MGH-HPS CGI
	Urine Pregnancy Test	PAERS

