The table below indicates the clinical ratings scheduled planned for the trial. If subjects' have significant ADHD, tic, anxiety or depression symptoms at screening, ratings of these symptoms will be followed regularly at study assessments. Subjects will be encouraged to continue outside therapy and will be required to continue all concurrent medications during the course of this trial. Subjects will also be asked about the number of missed doses of medications at each study visit.

Measure	Screening/ Baseline	Week 2	Week 4	Week 8	Week 12
CY-BOCS	X	X	X	X	X
DY-BOCS	X	X	X	X	X
YGTSS	X		X	X	X
ADHD-RS	X		X	X	X
CDI	X		X	X	X
MASC	X		X	X	X
MGH-HPS	X		X	X	X
CGI	X	X	X	X	X
PAERS	X	X	X	X	X
NAC dose	600mg BID	1200 mg BID	1200 mg BID	1200 mg BID	1200 mg BID

3. **Statistical Considerations:** Describe the statistical analyses that support the study design.

We will use the CY-BOCS as our primary outcome measure. Our primary analysis will involve a mixed effects model using weekly CY-BOCS ratings from baseline to 12 weeks with treatment (NAC/placebo) as a fixed factor and time as a within-subject factor. We will adhere to intention-to-treat principles in our analysis. We powered our study to have 80% power to detect a large effect of NAC ($d=0.9$) assuming $\alpha=0.05$. Given a similar variance in the Cy-BOCS scores in previous placebo-controlled trials of pediatric OCD, we would expect this effect size to correspond to a 6.5 point difference in Cy-BOCS between the NAC and placebo groups (POTS

HIC#1004006623

2004). By comparison, the effect size of NAC in the treatment of adults with trichotillomania, using the MGH-HS ($d=1.2$, $N=50$), and in bipolar depression, using the Montgomery-Asberg Depression Rating Scale (MADRS) ($d=0.8$, $N=80$) was considerably larger (Grant, Odlaug et al. 2008).

As a secondary outcome we will examine the safety and tolerability of NAC. Given our sample size of 40 we will have limited power to detect adverse events of low frequency. That being said, assuming that we do not see a side-effect in the placebo group, we will have 80% power to detect NAC related side-effect, if it occurs in one-third of NAC treated subjects. Frequency of side-effects will be measured with the PAERS as discussed in the assessments section.

SECTION VI: RESEARCH INVOLVING DRUGS, DEVICES, BIOLOGICS & PLACEBOS

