The clinical investigation of a drug product that is lawfully marketed in the United States may be exempt from the requirements for filing an IND. If there is no IND and an exemption is being sought, complete the following:

- i. Is the intention of the investigation to report to the FDA as a well controlled study in support of a new indication for use or to be used to support any other significant change in the labeling for the drug? Yes No
- ii. If the drug that is undergoing investigation is lawfully marketed as a prescription drug product, is the intention of the investigation to support a significant change in the advertising for the product? Yes No
- iii. Does the investigation involve a route of administration or dosage level or use in populations or other factor that significantly increases the risks (or decreases the acceptability of the risks) associated with the use of the drug product? Yes No

The NAC dosage for acute acetaminophen overdose is a 140mg/kg loading dose, followed by a maintenance dose of 70mg/kg administered every 4 hours for 17 consecutive doses. The dose used to treat acetaminophen overdose in children is approximately 10-fold greater than the maximum dose we will use in this study.

- iv. Will the investigation be conducted in compliance with the requirements for institutional (HIC) review and with the requirements for informed consent of the FDA regulations (21 CFR Part 50 and 21 CFR Part 56)? Yes No
- v. Will the investigation be conducted in compliance with the requirements regarding promotion and charging for investigational drugs? Yes No

2. **Background Information:** Provide a description of previous human use, known risks, and data addressing dosage(s), interval(s), route(s) of administration, and any other factors that might influence risks. If this is the first time this drug is being administered to humans, include relevant data on animal models.

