N-acetylcysteine (NAC) is generally well tolerated and has been extensively used at high doses in the treatment of acetaminophen overdose/toxicity for many years. The NAC dosage for acute acetaminophen overdose is a 140mg/kg loading dose, followed by a maintenance dose of 70mg/kg administered every 4 hours for 17 consecutive doses. The long-term use of NAC has also been investigated in six-month to three-year studies examining the efficacy and tolerability of NAC (dosed between 600-1200mg per day) in the treatment of chronic obstructive pulmonary disease COPD (Pela, Calcagni et al. 1999; Grandjean, Berthet et al. 2000; Stey, Steurer et al. 2000; Kasielski and Nowak 2001; Poole and Black 2001; Chikina, Iagmurov et al. 2002; Decramer, Rutten-van Molken et al. 2005). A recent study by Decramer and colleagues in 2005 concluded that there were no adverse events thought to be drug related in their study examining the use of 600mg/day of NAC in over 500 patients with COPD. Additionally, Chikina and colleagues found that the most effective dose of NAC in the treatment of COPD was 1200mg/day (the study examined doses of NAC ranging from 600-2400mg/day). A meta-analysis examining the efficacy of NAC in COPD, performed in 2000, revealed that NAC was well tolerated without significant adverse effects (Grandjean, Berthet et al. 2000). Although generally well-tolerated, the PDR indicates that adverse reactions reported with oral NAC include nausea, vomiting, diarrhea, headache (especially when used along with nitrates) and rashes. There are rare reports of renal stone formation. It is also important to note that rare reports of bronchoconstriction have occurred with intravenous NAC (but no reports of bronchospasm related to the oral use of NAC). Although there are no known contraindications to

NAC use, individuals with asthma will be excluded from the study given the rare, but potential, adverse effect of bronchospasm.

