The safety and tolerability of chronic NAC at higher doses has been evaluated in a number of contexts. In a double-blind, placebo-controlled randomized trial of oral NAC in HIV-infected patients, subjects were treated with 8,000mg per day of NAC for 8 weeks (De Rosa et al, 2000). Adverse effects in this trial were minimal and some subjects reduced the dose due to side effects, with the average dosage by the end of the trial being 6.3 grams/day; however, the reduction in "dose" was similar for the placebo arm. In another double-blind, placebo-controlled randomized trial involving 43 Alzheimer's patients, subjects were given placebo or 50 mg/kg/day orally (Adair, Knoefel et al. 2001). In that study, there were no adverse effects more common than in placebo (except perhaps headache).

In acetaminophen overdose, the dose of NAC is 140 mg/kg load followed by 70 mg/kg every 4 hours for 17 consecutive doses. At this dosage, NAC can cause nausea, vomiting and sometimes generalized urticaria. In normal volunteers the dose that the vast majority of patients were able to tolerate was 3200 mg/m²/day. Common toxicities at higher doses were bad taste and gastrointestinal disturbances (Pendyala and Creaven. et al).

Severe toxicity is rare and occurs at doses an order of magnitude higher than what we will be using in this study. In a single case report, a 16-kilogram child received 39,207 mg of intravenous NAC due to a medical error; she developed cerebral edema with uncal herniation (Bailey, Blais et al. 2004). The lethal oral dose of NAC is 4400 mg/kg in mice and 5050 mg/kg in rats (RTECS 2001).

According to the PDR: "NAC is rapidly absorbed from the gastrointestinal tract and transported to the liver via the portal circulation, where it undergoes extensive first-pass metabolism. Peak plasma concentrations are observed approximately 0.5 to 1 hour following oral administration of doses of 200 to 600 milligrams. NAC is metabolized to N-acetylcysteine, N, N-diacetylcysteine and L-cysteine. L-cysteine itself is metabolized to glutathione, protein, taurine and sulfate. NAC has low bioavailability, probably because of its extensive first-pass metabolism in the liver. The terminal half-life of total NAC is approximately 6.25 hours after ingestion. Use of supplemental NAC along with carbamazepine may cause reduced serum levels of carbamazepine."

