In many cases subjects will be screened via telephone. The telephone screen will be used to inform the parent (primary caretaker) about the nature of the study, the duration of the study, number of visits, randomization, etc. The telephone screen will include collecting a brief history to exclude subjects that are unlikely to be eligible. People may not be eligible because of an ongoing medical problem (asthma or pregnancy), presence of an excluded psychiatric diagnosis (see exclusion criteria), or because they are unable to attend scheduled study visits. Interested subjects will be scheduled for a screening visit. The screening visit will occur over one visit. The overall purpose of the screening is to confirm that the subject meets all entry criteria. The first step in the screening visit will be to review the consent form, answer questions about the protocol and to obtain written informed consent. All procedures will be described to the subject in a developmentally appropriate manner.

2. **Inclusion/Exclusion Criteria:** What are the criteria used to determine subject inclusion or exclusion? How will eligibility be determined, and by whom?

Subjects will be well-characterized and must meet selection criteria to be enrolled. The measures used in the baseline assessment will be used by the principal investigators to determine if subjects meet inclusion/exclusion criteria.

Inclusion Criteria:

1. Children aged 8-17 years.
2. Primary diagnosis of OCD.
3. Duration of OCD greater than 6 months.
4. Significant Current OCD symptoms: Current CY-BOCS score greater than or equal to 16.

Exclusion Criteria:

1. Comorbid bipolar disorder, psychotic disorder, substance use disorder, developmental disorder or mental retardation (IQ<70).
2. Recent change (less than 4 weeks) in medications that have potential effects on OCD severity (such as Selective Serotonin Reuptake Inhibitors, clomipramine, naltrexone, lithium, psychostimulants, anxiolytics, or antipsychotics). Medication change is defined

to include either dose changes or medication discontinuation.

3. Asthma requiring medication use within the last 3 months (case reports have linked intravenous NAC administration with asthma exacerbation)
4. Known hypersensitivity or previous anaphylactoid reaction to acetylcysteine or any components in its preparation.
5. Positive pregnancy test or drug screening test.
6. Previous use of N-acetylcysteine (dose greater than 600mg for more than 2 weeks).

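### The protocol says NAC may lower carbamazepine levels, but no eligibility, concomitant-medication or monitoring rule in the supplied text acts on it

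*Combined protocol and SAP*

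**What the plan says.** Section VI, item 2 (Background Information) is where the form asks for "known risks, and data addressing dosage(s), interval(s), route(s) of administration, and any other factors that might influence risks". The answer ends its pharmacology paragraph, taken from the PDR, with: "Use of supplemental NAC along with carbamazepine may cause reduced serum levels of carbamazepine". Carbamazepine is not mentioned anywhere else in the supplied text.

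The rules that decide who enters and what they take are these:

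- **Phone screen** (Section V, item 3, pre-study screening). The medication-related exclusion is "a change in psychotropic medications or behavioral treatment for OCD within the last month".
- **Exclusion criterion 2** (Section VII, Inclusion/Exclusion Criteria). It bars "Recent change (less than 4 weeks) in medications that have potential effects on OCD severity". The drugs named after it are examples, and a change covers dose changes and discontinuation.
- **Concurrent treatment** (Section V, item 3, above the visit schedule). Subjects "will be required to continue all concurrent medications during the course of this trial".
- **Medical assessment** (Section V, item 3): "A medical assessment including vital signs, physical exam and urine drug screen and pregnancy test will be completed prior to study enrollment". The visit schedule that follows contains rating scales and the study drug dose only.
- **After week 12** (Section V, item 3, Intervention): "After completion of the study all subjects receiving placebo will be offered NAC treatment for the following 12 weeks". Section VI, item 7 describes the same offer.

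The risk text in Section IX, items 1 and 2, covers NAC side effects, symptom worsening, rating burden and unanticipated effects. It does not mention the interaction.

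**The concern.** The protocol names a possible effect of the study drug on another medicine and then has no instruction for a child who takes that medicine. Its own eligibility and continuation rules would bring about the combination it warns of.

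What is at stake is the safety of an individual child. If the carbamazepine level fell, the first sign might be poorer control of whatever carbamazepine was treating. Blinded staff might not connect that with study drug. The Section IX argument that symptom worsening is probably no likelier than on current medication alone treats that medication as unaffected by NAC. For carbamazepine, Section VI says it may not be.

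**Working it through.** The plan gives no figure on this point, so the main check sets its rules side by side for one hypothetical child: aged 8 to 17, primary OCD, CY-BOCS of at least 16, otherwise eligible, and on an unchanged dose of carbamazepine for more than a month.

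1. *Phone screen.* There has been no medication change in the last month, so the child passes.
2. *Exclusion criterion 2.* There has been no change within 4 weeks, so the child passes. Whether carbamazepine belongs among drugs that may affect OCD severity makes no difference, because stable use passes either way.
3. *Other exclusions.* Bipolar, psychotic, substance use and developmental disorders are excluded. Epilepsy is not listed.
4. *During the trial.* Concurrent medications must be continued, so carbamazepine continues. That rule is sensible in itself.
5. *Monitoring.* The listed laboratory tests are urine tests. Planned carbamazepine levels: 0.
6. *Exposure.* With 1:1 allocation the child has a 20/40 = 50% chance of blinded NAC. The planned dose is 1200 mg/day for 7 days, then 2400 mg/day for 12 × 7 − 7 = 77 days. A child on placebo is offered NAC for 12 weeks afterwards, so the combination can arise in either arm.

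**How many children?** The documents give no rate of carbamazepine use. Let *r* be the rate per enrolled child; every value of *r* below is an assumption with no anchor in the protocol. Inputs from the protocol are 40 children and 1:1 allocation, hence 20 on blinded NAC. Expected users = 40*r*; chance of at least one user = 1 − (1 − *r*)^40; chance of at least one on blinded NAC = 1 − (1 − *r*)^20.

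| Assumed *r* | Expected users of 40 | Any user of 40 | Any user among 20 on NAC |
|---|---|---|---|
| 0 | 0 | 0% | 0% |
| 0.25% | 0.1 | 10% | 5% |
| 0.5% | 0.2 | 18% | 10% |
| 1% | 0.4 | 33% | 18% |

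Zero users is more likely than not as long as *r* is below 1 − 0.5^(1/40) = 1.7%. The table only converts an assumed rate into a count; it is not evidence about the rate.

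The consequence for a child who did take both drugs cannot be sized, because the documents do not say how far the level may fall.

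**The case against.** The strongest reply is that this is a true omission of little consequence. The source is one hedged sentence with no size, dose or clinical outcome. The interaction is disclosed where the form asks for known risks, so the reviewing committee could see it. General safeguards exist:

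- medical history is taken at baseline;
- participation is discussed with the primary clinician and/or pediatrician, whose opinion is documented (Section VIII, item 2);
- the PAERS is completed at every visit;
- the clinician may reduce the study drug dose (Section IX, item 2);
- adverse events are reviewed at least quarterly.

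In a single-site trial of about 40 children, handling a rare co-medication case by case is a reasonable way to work.

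Most of this stands, and it is why the point is minor. What it does not answer is that none of these safeguards is triggered by carbamazepine use. Dose reduction responds to a suspected drug-related adverse effect, which a falling level need not resemble. The clinician consulted may not be the carbamazepine prescriber.

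A reader might infer more than the documents support:

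- *That NAC is contraindicated with carbamazepine, or that a child would be harmed.* The protocol states a possible level change and says there are no known contraindications to NAC.
- *That the protocol breaks its own standard.* It says "individuals with asthma will be excluded from the study given the rare, but potential, adverse effect of bronchospasm", although it reports bronchospasm only with intravenous use. That shows it will exclude as a precaution; it does not mean every listed interaction needs an eligibility rule.
- *That families are not warned.* The consent and assent forms and some other pages were not available, so nothing can be said about them.
- *That the CY-BOCS comparison is biased.* Nothing in the documents points to this.

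One could also object that excluding at entry but only notifying later is uneven. The two situations differ: before randomization, exclusion leaves the child's treatment as it was, whereas a child already in the trial is better kept under follow-up. The later rule must, however, be the same in both arms and both periods.

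**Conclusion.** The concern holds as a minor individual-safety gap, worth considering because it is so cheap to close. In the supplied text the interaction is stated once, and no eligibility, concomitant-medication or monitoring rule acts on it. A child on stable carbamazepine is eligible, must continue it and has no level check.

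Confidence is high for that textual omission only. It most likely affects no child among 40, a judgement that rests on low carbamazepine use in this population. The exclusion of bipolar and developmental disorders makes low use plausible, but the documents do not quantify it. The clinical consequence is unknown because the level reduction has no stated size. No effect on the CY-BOCS comparison is expected, and the sample size calculation is untouched.

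**What to change.** Amend the protocol as follows.

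1. Add *current use of carbamazepine* to the exclusion criteria in Section VII and to the phone screen in Section V. State that carbamazepine must not be stopped in order to qualify, in keeping with the Section VII assurance against withdrawing current medication for the sake of participation.
2. List the interaction among the risks in Section IX.
3. For any child who starts carbamazepine during the trial, or before taking up the post-trial NAC offer, notify the carbamazepine prescriber of the interaction before study drug or NAC is given or continued. Apply the same rule in both arms and both periods. It needs no unblinding, and stopping study drug is not mandated.

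Level monitoring is not required. It would add blood tests to a trial that otherwise lists none, and a falling level could hint at allocation.

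The cost is one exclusion line, one phone-screen item, one notification sentence and one Section IX sentence. The downside is the loss of any otherwise eligible carbamazepine user: probably none, and 0 to 0.4 of 40 expected under the assumed rates.
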